Figure 1. IPERGAY Study: Time to first STI (panel a), GC infection (panel b), CT infection (panel c), and syphilis infection (panel d) ¹

begun to prescribe doxycycline PEP to reduce incident STIs in MSM without a confirmatory study or normative guidance. Moreover, the balance of benefits and risks of doxycycline PEP need to be carefully studied in MSM living with HIV as well as in PrEP users in a study powered to assess effectiveness for each population. The relative benefits and risks of doxycycline PEP may differ in MSM living with HIV and PrEP users due to differences in adherence, sexual practices, potential risk compensation, sexual networks, and/or pre-existing antibiotic resistance due to higher prior antibiotic exposure among MSM living with HIV.

In summary, a sufficiently-powered, high-quality study is needed to evaluate the effectiveness of doxycycline PEP in populations both with and without HIV infection, and to evaluate its impact on drug resistance in target bacterial STIs and resident bacterial microbiota. There is a public health need and sufficient clinical equipoise to conduct an effectiveness study of doxycycline PEP as an STI reduction strategy for a diverse population of MSM in the US to address the following key scientific questions: 1) Effectiveness of doxycycline PEP for bacterial STI prevention in MSM and TGW on PrEP, 2) Effectiveness of doxycycline PEP in MSM and TGW living with HIV; 3) Differential tolerability and impact on antimicrobial resistance between MSM/TGW living with HIV and MSM/TGW on PrEP; 4) TCN resistance in GC, CT and syphilis, 5) TCN resistance in commensal Neisseria (which can transfer TCN resistance) and potentially pathogenic Staph Aureus in carriers, and 6) effect on the gut resistome in terms of changes in TCN resistance genes.

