3.4. Randomization

The randomization is 2:1 for assignment to doxycycline PEP versus standard of care (no doxycycline PEP). Randomization is stratified by four sites, two primarily enrolling HIV-infected, and two HIV-uninfected participants, with block sizes selected with size randomly selected from between 15 to 30.

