7. EFFICACY

7.1. General Considerations

Tabulations will be by study arm within each cohort, for each quarter of study follow-up (or at visits where evaluated). These will be reported in only the closed report during the study. Parallel tabulations will be given by study site only if substantive differences are observed between sites (which are not expected).

Inferential statistical tests will be two-sided and will be performed at alpha levels of 0.05 and 0.10 to declare the significance of main effects and interaction effects, respectively.

Analyses will be conducted separately for HIV-infected and HIV-uninfected cohorts for the primary endpoint, and for the combined cohort. All secondary endpoints will be conducted in the combined cohort.

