7.5.5. Analysis of Tetracycline resistance

7.5.5.1. Primary analysis of TCN resistance in GC cases

The primary analysis of TCN resistance in GC will be conducted in the GC positive.

Descriptive statistics: Tabulations of resistance amongst cases (GC: TCN resistance testing missing, not resistant, resistant) will be reported at baseline, month 3, 6, 9, and 12 (and potentially interim visits) in each arm, for any infection site, and broken out by infection site. Additional descriptive information may also be included (i.e. change in MIC in GC cultures amongst those with repeat infections)

Statistical analysis: Assessment of odds of resistance amongst GC cases with resistance results will be assessed by arm using logistic regression with arm as exposure, adjusted for city. To account for repeated infections, repeated measures methods (GEE) will be used. Analysis comparing arms also potentially adjusted for age, race/ethnicity, baseline STI, baseline and follow-up sexual risk (number of partners, unprotected anal sex, employment). For the HIV-negative cohort, PrEP at baseline; for the HIV-positive cohort, viral suppression at baseline will also be considered.

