7.5.5.4. Analysis of TCN resistance in *S. aureus* carriers

The primary analysis of TCN resistance will be conducted in *S. aureus* cases detected at Baseline, 6- and 12-month visits.

Outcome: TCN resistance will be a dichotomous outcome defined as sensitive or resistance, based on e-Test cut-offs.

Descriptive statistics: Tabulations of TCN resistance in *S. aureus* cases (TCN resistance testing missing, not resistant, resistant) will be reported at baseline, 6- and 12-month visits in each arm. (site of *S. aureus*, if found, will not be known).

Statistical analysis: Assessment of difference in prevalence of TCN resistance by arm at each of 6 and 12 months will be assessed by estimating the relative risk of TCN resistance using modified Poisson regression. The model will assess the relative risk of resistance by arm, adjusted for study site at each time point. If an effect is found, assessment of a trend in time will be assessed by fitting a linear trend over study time. If prevalence of resistance is < 5%, analysis will pool across visits.

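### The combined-cohort GC tetracycline-resistance model commits to adjustment for city but not for HIV cohort, so a difference between arms in the cohort mix of GC cases can bias the odds ratio slightly (minor)

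*SAP*

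**What the plan says.** GC resistance in culture is listed as a primary endpoint (SAP 2.2.1.2). SAP 7.5.5.1 plans a logistic model with GEE for repeat infections, in which the odds of resistance "will be assessed by arm using logistic regression with arm as exposure, adjusted for city". Further covariates are left open: "Analysis comparing arms also potentially adjusted for age, race/ethnicity, baseline STI", followed by sexual-risk variables. For the HIV-negative cohort it adds baseline PrEP, and "for the HIV-positive cohort, viral suppression at baseline will also be considered". Neither site nor HIV cohort appears in the committed or the optional list.

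Other parts of the SAP bear on this:

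- **Randomisation (3.4).** "Randomization is stratified by four sites, two primarily enrolling HIV-infected, and two HIV-uninfected participants". Allocation is 2:1.
- **Sister models.** The primary STI model (7.5.1) has site and arm as covariates, and the CT and syphilis resistance models (7.5.5.2, 7.5.5.3) adjust for site. For S. aureus (7.5.5.4), "The model will assess the relative risk of resistance by arm, adjusted for study site at each time point".
- **Cohorts (7.1).** "Analyses will be conducted separately for HIV-infected and HIV-uninfected cohorts for the primary endpoint, and for the combined cohort". Secondary endpoints are analysed in the combined cohort. Section 7.5.5.1 does not say which rule applies to GC resistance, and SAP 5.2.4 defines a single GC-positive population.

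The protocol (4.3) shows one HIV clinic and one STI clinic with a PrEP programme in each city.

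**The concern.** City pools an HIV clinic with a PrEP clinic, so it carries almost no information on HIV cohort. Randomisation balances cohort among everyone randomised, but not among those who go on to acquire GC. If doxycycline prevents GC better in one cohort, that cohort is under-represented among GC cases in the doxycycline arm. If background resistance also differs by cohort, the arms differ in resistance even when doxycycline selects for none.

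The protocol raises both conditions. Section 2 gives possible differences in background resistance and in effectiveness as reasons to power the cohorts separately. Section 1.1 mentions "pre-existing antibiotic resistance due to higher prior antibiotic exposure among MSM living with HIV".

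At stake is a primary safety question. A cohort-mix artefact could be read as selection for resistance or, in the other direction, could mask it.

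**Working it through.** **1. The plan's expected number of GC cases.** Inputs from Protocol 10.2: 520 doxycycline and 260 control participants over both cohorts, four quarters, 5% GC per quarter in controls, 35% effectiveness, 10% loss.

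- Doxycycline: 520 × 4 × 0.05 × 0.65 × 0.9 = 60.8
- Control: 260 × 4 × 0.05 × 0.9 = 46.8

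This reproduces the stated 61 versus 47, or 108 in total. It is an upper figure for the resistance model, because not every case will yield a culture result.

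**2. Bias of the city-only model.** Assumptions, since the documents give no cohort-specific figures:

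- Control GC cases split 50:50 between cohorts, with the same mix in both cities.
- No effect of doxycycline on resistance within either cohort.
- Resistance p1 = 25% and p2 = 38%. These are the ends of the range in Protocol 1.2.3, which is a range across studies of MSM and not a contrast between HIV cohorts.
- Cohort GC risk ratios r1 and r2.

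Then:

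- Control resistance: pc = (p1 + p2)/2 = 31.5%
- Doxycycline resistance: pd = (r1·p1 + r2·p2)/(r1 + r2)
- OR = [pd/(1 − pd)] / [pc/(1 − pc)]
- SE of log OR = √[1/(61·pd(1 − pd)) + 1/(47·pc(1 − pc))]
- Two-sided error = P(|Z + ln OR/SE| > 1.96)

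The risk ratios in this table all average 0.65, the planned overall effect.

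| r1 / r2 | pd | OR | SE | Two-sided error |
|---|---|---|---|---|
| 0.65 / 0.65 | 31.5% | 1.00 | 0.418 | 5.0% |
| 0.55 / 0.75 | 32.5% | 1.05 | 0.416 | 5.1% |
| 0.50 / 0.80 | 33.0% | 1.07 | 0.416 | 5.3% |
| 0.35 / 0.95 | 34.5% | 1.15 | 0.414 | 6.2% |

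A more extreme split is 65% versus 0% effectiveness:

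- pd = (0.35 × 0.25 + 1.00 × 0.38)/1.35 = 34.6%, OR 1.15.
- Of 108 isolates, 108 × 2.70/4.70 = 62 would be in the doxycycline arm and 46 in control, giving a two-sided error of 6.3%.
- If the better-protected cohort has the higher resistance, pd = (0.35 × 0.38 + 1.00 × 0.25)/1.35 = 28.4% and the OR is 0.86.

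**3. Size against precision.** With SE about 0.42, exp(1.96 × 0.42) ≈ 2.3, so the 95% CI spans a factor of about 2.3 either way.

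**4. Stress case.** Protocol 1.1 gives 55% as the European resistance level. With 25% versus 55% between cohorts, the three unequal rows of the table give ORs of 1.10, 1.15 and 1.33 and errors of 5.7%, 6.5% and 11.1%. This contrast lies beyond the US range that the protocol quotes.

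**5. Which term removes the bias.** Logistic models were fitted to the expected counts for the three unequal rows.

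| Adjustment | OR at 25%/38% | OR at 25%/55% |
|---|---|---|
| City | 1.05–1.15 | 1.10–1.33 |
| Four sites, each purely one cohort | 1.00 | 1.00 |
| Four sites, each 85% one cohort | 1.02–1.08 | 1.05–1.17 |
| City + HIV cohort | 1.00 | 1.00 |

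**6. Feasibility.** This was simulated with 3,000 datasets per scenario, without repeat infections. City plus cohort failed to fit in 0–0.6% of datasets at 54 or more isolates and in 8–12% at 27, where city alone failed in 4–5%. Four site terms failed in 7–17% at 54 isolates and in 46–56% at 27.

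**The case against.** The strongest reply is that 7.5.5.1 itself expects by-cohort models. Baseline PrEP and viral suppression each make sense in one cohort only, and 7.1 requires by-cohort analysis of the primary endpoint. Within a cohort there is no cohort mix to shift, and city is nearly the same as site. This stands: the by-cohort results are largely unaffected. It does not remove the combined model, because 7.1 leads to a combined fit whether GC resistance is classed as primary or secondary.

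Second, the bias needs two differences at once. The protocol raises them only as possibilities and plans a single 35% GC effectiveness, under which the bias is zero. This also stands, and it limits the point to protection against a contingency.

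A reader might go further and infer that the false-positive rate doubles. In the 65%/0% scenario the simulated one-sided error in the direction of harm was 5.4% against 2.5% at 108 isolates. But SAP 7.1 specifies two-sided tests, the split is extreme, and on the plan's convention the error is 6.3% against 5%.

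A reader might also infer that copying the site term from the sister models is a full cure. SAP 3.4 says that sites only primarily enrol one cohort, so a site term leaves residual bias where sites are mixed.

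**Conclusion.** The point holds for the combined-cohort model only, and it is minor. The GC resistance model is the one model among its peers that does not commit to site, and it offers no route to HIV cohort. Under assumed resistance of 25% and 38%, the spurious OR is about 1.05 to 1.15, or about 0.86 to 0.95 if the direction reverses. Two-sided error is about 5.1% to 6.3% at about 108 isolates. The bias vanishes if resistance or GC effectiveness is equal across cohorts.

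The documents do not support concluding that the resistance result is untrustworthy for this reason: the bias is small beside the expected confidence interval, and its inputs are assumptions. Nor would a cohort term make the case-only comparison unbiased. Conditioning on GC infection is a separate and potentially larger problem. If doxycycline prevented only susceptible GC, a 35% overall effect would raise resistance among cases from 25% to 0.25/0.65 = 38.5% (OR 1.9), or from 38% to 0.38/0.65 = 58.5% (OR 2.3).

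**What to change.** In SAP 7.5.5.1, replace the adjustment for city with wording such as: *The GC resistance model will be fitted in each HIV cohort, adjusted for city, and in the combined cohort, adjusted for city and HIV cohort as separate terms. A combined model with four-level study site will be a sensitivity analysis.* The primary covariate set should be fixed in advance and not chosen according to which model converges. The change should be dated in SAP section 10.

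Both variables are already collected, so only wording changes. In the simulation, adding cohort to city raised the SE of the log OR by about 2–7% at 54 or more isolates and by about 6–9% at 27, where fitting failures also become more common. The selection effect of analysing GC cases only needs its own treatment.

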7.5.5.2. Analysis of TCN resistance in CT cases

The analysis of TCN resistance in CT cases will be conducted in all persons with a positive CT diagnosis after baseline.

Outcome: Molecular TCN resistance will be defined as presence of mutations associated with TCN resistance in the CARD database.

Descriptive statistics: Tabulations of TCN resistance in CT cases (TCN resistance testing missing, not resistant, resistant) will be reported at baseline, 3-, 6-, 9-, and 12-month visits in each arm.

Statistical analysis: Assessment of difference in prevalence of TCN resistance by arm across all post-baseline visits combined will be assessed by estimating the relative risk of TCN resistance using logistic regression. The model will assess the relative odds of resistance by arm, adjusted for study site.

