1.2.3 Potential for drug resistance

An important consideration with intermittent doxycycline use for STI prophylaxis is selection of drug resistance, in both target bacterial STI pathogens as well as in microbiota which are potential pathogens or possible reservoirs of antimicrobial resistance, such as *S. aureus* and commensal *Neisseria* species. GC has sequentially developed resistance to antibiotics in multiple classes, including those previously or currently recommended for treatment. Rates of TCN-resistance in GC in the US are 25%-38% in studies of MSM,¹¹ compared with >50% in Europe.²⁰ Doxycycline is not currently recommended as treatment for GC. IPERGAY has not reported on TCN resistance in GC and did not address AMR in other bacterial such as *S. aureus* and commensal *Neisseria* species. Doxycycline is commonly used to treat CT and syphilis, and there have been no documented cases of TCN-resistant CT or syphilis. However, TCN resistance from single point mutations has been reported in related organisms such as *Chlamydia suis^{38, 39}* and *Brachyspira spp.⁴⁰* in antibiotic-exposed pigs, suggesting that development of TCN resistance could evolve (or be acquired from a resistant organism such as *E. coli*⁴¹). Azithromycin-resistant *Treponema pallidum* emerged from a single mutation⁴² and rapidly became widespread in the US west coast and globally,⁴³ serving as a cautionary tale.

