10.2 Statistical power and analysis

Primary endpoint: We selected a sample size for each cohort (MSM/TGW living with HIV and MSM/TGW on PrEP) to achieve 80% power with 0.05 two-sided Type 1 error, for the endpoint of any lab-detected incident early syphilis, GC and/or CT infection, based on quarterly assessments for each person, 10% annual loss to follow-up and an intra-class correlation of 0.2, reflecting the high prevalence of STI re-infection that has been observed in these populations. With these assumptions, a cohort of approximately 390 of MSM/TGW living with HIV and 390 of MSM/TGW on PrEP (130 in the control and 260 in the intervention for each cohort) will provide 80% power to detect a decrease in guarterly STI prevalence from 10% to 5%, which corresponds to an annual reduction in combined STI incidence from 34% to 19% (Table 10.2.1). With allowance for 10% lost to follow-up, the sample size for each cohort will be approximately 390 participants, for a total sample size of 780. Based on 2017 STI incidence data from San Francisco and Seattle PrEP cohorts for both GC and CT, we expect in the control arm in each quarter approximately 5% of participants to have GC, 5% CT and 2% early syphilis, acknowledging some will be diagnosed with more than one infection. Based on the higher susceptibility of GC to TCN in the US vs France (75% vs < 50%^{11, 20}) and the 70% reduction of CT and syphilis with PEP in IPERGAY,¹ we anticipate effectiveness of doxycycline PEP to be 35% for GC, 65% for CT and 65% for syphilis. Given these assumptions, with a 2:1 randomization we expect to see 61 vs 47 GC infections, 47 vs 33 CT infections and 19 vs 13 syphilis infections in the doxycycline PEP and control arms respectively, some of which will occur in the same individuals. Sample sizes were computed using nQuery for repeated measures for two proportions. The analysis will compare time-averaged proportion of infections in each guarter between arms, using repeated measure methods.

Table 10.2.1: Power Table for N = 390; 2:1 randomization doxycycline PEP: SOC. Sample size assumes 370 fully evaluable participants.

Control arm quarterly	Intervention arm quarterly	Power to detec	t 50% reduction	Power to detect 65% reduction	
prevalence	prevalence	ICC = 0.2	ICC = 0.1	ICC = 0.2	ICC = 0.1
10%	5%	80%	87%	96%	99%
7.5%	3.75%	68%	76%	90%	95%
5%	2.5%	51%	59%	77%	85%
3%	1.5%	35%	41%	57%	65%
2%	1%	26%	30%	43%	50%

DoxyPEP protocol Ver 9.0 5/27/2022

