7.5.5.3. Analysis of TCN resistance in Syphilis cases

The analysis of TCN resistance in Syphilis cases will be conducted in all persons with an incident syphilis cases after baseline.

Outcome: Molecular TCN resistance will be defined as presence of mutations associated with TCN resistance in the CARD database.

Descriptive statistics: Tabulations of TCN resistance in Syphilis cases (TCN resistance testing missing, not resistant, resistant) will be reported at baseline, 3-, 6-, 9-, and 12-month visits in each arm.

Statistical analysis: Assessment of difference in prevalence of TCN resistance by arm across all post-baseline visits combined will be assessed by estimating the relative risk of TCN resistance using modified Poisson regression. The model will assess the relative risk of resistance by arm, adjusted for study site.

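### The CT resistance analysis mismatches model and estimand, and neither the CT nor the syphilis resistance analysis says how repeat infections or zero resistant cases will be handled

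*SAP*

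**What the plan says.** SAP 7.5.5.2 (CT) compares the prevalence of TCN resistance by arm "across all post-baseline visits combined". Its model text reads "estimating the relative risk of TCN resistance using logistic regression. The model will assess the relative odds of resistance by arm", with site as a further covariate. SAP 7.5.5.3 (syphilis) pools visits in the same way and plans "estimating the relative risk of TCN resistance using modified Poisson regression. The model will assess the relative risk of resistance by arm". The outcome in both is molecular: "Molecular TCN resistance will be defined as presence of mutations associated with TCN resistance in the CARD database".

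The neighbouring sections contain what these two lack. For gonorrhoea (GC), SAP 7.5.5.1 states: "To account for repeated infections, repeated measures methods (GEE) will be used". For *S. aureus*, SAP 7.5.5.4 pools visits if the prevalence of resistance is below 5%.

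Two statements in the protocol bear on how the CT and syphilis models will behave. Section 1.2.3 says "there have been no documented cases of TCN-resistant CT or syphilis". Section 10.2 chose an intra-class correlation (ICC) of 0.2, "reflecting the high prevalence of STI re-infection that has been observed in these populations".

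**The concern.** There are three separate gaps.

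1. **Estimand (CT only).** The text names a relative risk, a logistic model and relative odds in two consecutive sentences. It mentions no conversion from odds to risk, so two analysts could report different quantities.
2. **Repeat infections (both).** Visits are combined and re-infection is expected, but no clustering method is named and the unit of analysis (infection, visit or participant) is not stated.
3. **Sparse cases (both).** Where resistance is expected to be rarest, there is no fallback for an arm with no resistant case.

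The third gap matters most. A ratio model with an empty arm has no finite estimate, and the output can mislead rather than merely fail. Resistance is central to the risk-benefit judgement that the protocol wants to inform, so a spurious signal from one or two infections would do harm. So would losing the useful statement of how much resistance the data can exclude.

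**Working it through.** **Inputs.** Protocol 10.2 and SAP 3.3.1 give 260 doxycycline and 130 control participants per cohort, hence 520 and 260 in total; four quarterly visits; 10% loss to follow-up; control rates per quarter of 5% GC, 5% CT and 2% syphilis; and effectiveness of 35%, 65% and 65%. No prevalence of resistance mutations is given, so the values used below are assumptions.

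**Step 1: infections available for testing.** Expected infections = N × 0.9 × 4 × quarterly rate × (1 − effectiveness).

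| | Doxycycline | Control | Protocol 10.2 (doxycycline vs control) |
|---|---|---|---|
| GC | 520×0.9×4×0.05×0.65 = 60.8 | 260×0.9×4×0.05 = 46.8 | 61 vs 47 |
| CT | 520×0.9×4×0.05×0.35 = 32.8 | 46.8 | 47 vs 33 |
| Syphilis | 520×0.9×4×0.02×0.35 = 13.1 | 260×0.9×4×0.02 = 18.7 | 19 vs 13 |

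GC reproduces as printed. CT and syphilis reproduce only with the arms interchanged, so the printed order appears to be reversed. The figures below use 33 doxycycline and 47 control CT infections, and 13 and 19 syphilis infections.

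**Step 2: chance that at least one arm has no resistant infection.** With prevalence p in both arms, and infections treated as independent, this is 1 − [1 − (1−p)^n₁][1 − (1−p)^n₀]. For CT at 1%: 0.99³³ = 0.718 and 0.99⁴⁷ = 0.624, so 1 − 0.282 × 0.376 = 0.894.

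| Assumed p | CT: expected resistant | CT: empty arm | Syphilis: expected resistant | Syphilis: empty arm |
|---|---|---|---|---|
| 0.5% | 0.4 | 97% | 0.16 | 99% |
| 1% | 0.8 | 89% | 0.32 | 98% |
| 2% | 1.6 | 70% | 0.64 | 93% |
| 5% | 4.0 | 26% | 1.6 | 70% |

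**Step 3: what the models return with an empty arm.** These are test fits with arm as the only covariate; adding an arbitrary two-level site term left the picture unchanged.

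| Data | Model | Log-ratio | Robust SE | Model-based SE | Fisher p |
|---|---|---|---|---|---|
| CT 2/33 vs 0/47 | Logistic | 20.8 | 0.73 | about 11,600 | 0.17 |
| CT 2/33 vs 0/47 | Poisson | 21.6 | 0.69 | about 17,400 | 0.17 |
| Syphilis 1/13 vs 0/19 | Logistic | 21.1 | 1.04 | about 18,200 | 0.41 |
| Syphilis 1/13 vs 0/19 | Poisson | 20.6 | 0.96 | about 14,900 | 0.41 |

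The log-ratio is only the point at which the iteration stopped. With model-based errors the interval is uselessly wide. With the robust errors of modified Poisson, 21.6/0.685 is a z of about 31, hence p below 10⁻²⁰⁰. The Fisher value for CT is C(33,2)/C(80,2) = 528/3160 = 0.167.

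**Step 4: what an exact summary gives.** With 0 of n resistant, the upper limit of the two-sided 95% interval is 1 − 0.025^(1/n): 10.6% (n = 33) and 7.5% (47) for CT, and 24.7% (13) and 17.6% (19) for syphilis. With none in control, four resistant infections under doxycycline are needed for Fisher p < 0.05: 4/33 gives 0.026 where 3/33 gives 0.066, and 4/13 gives 0.020 where 3/13 gives 0.058.

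**Step 5: repeat infections.** Spreading infections over four visits with a beta-binomial at ICC 0.2 puts about 80 CT infections in about 58 participants (24 doxycycline, 34 control) and about 32 syphilis infections in about 24 (10 and 14). If resistance were fully shared within a person, the design effect would be about 1.6 to 1.7. With one record per participant, the zero-case limits widen to 14.2% and 10.3% for CT and 30.8% and 23.2% for syphilis.

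**Step 6: odds against risk.** For a relative risk of 2, the odds ratio is 2.02 at 1% control prevalence, 2.11 at 5% and 3.00 at 25%.

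**The case against.** The strongest reply is that little is lost in practice. If resistance is rare, the odds ratio and relative risk nearly coincide (Step 6), and with one or two cases clustering hardly matters. That stands: the CT mismatch is mainly a specification error, and the three gaps do not add up to three times the harm.

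A reader might infer that neither planned model can deliver its stated result. The documents do not support this. Syphilis pairs a relative risk with modified Poisson, which is coherent, and a relative risk can be derived from a logistic model by standardisation, although the SAP does not mention it.

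A reader might also infer that zero or one resistant case is the protocol's expectation. It is not stated. The protocol speaks of documented resistance, while the SAP outcome is any listed mutation, and Protocol 10.2 itself says the clinical significance of such mutations is less clear. Mutations may be more common than clinical resistance, so a range is needed. At 5%, an empty arm for CT is the exception.

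Nor is it right that the plan would necessarily yield no interval or no useful information. Robust errors give an interval that is falsely narrow, and both sections already plan counts by arm and visit, though without confidence limits.

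On repeat infections, the SAP can be read more kindly. It analyses persons with a diagnosis, sections 5.2.5 and 5.2.6 define participant populations, and 7.5.1 introduces modified Poisson with GEE. The text is silent rather than shown to be wrong. Even so, one record per person leaves open which infection is kept.

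**Conclusion.** The point holds in limited form. SAP 7.5.5.2 contradicts itself on the CT estimand. Sections 7.5.5.2 and 7.5.5.3 both leave the unit of analysis and the handling of repeat infections unstated, and both lack a rule for sparse cases. The sparse-case gap carries the weight: at an assumed prevalence of 1% to 2%, an empty arm has a chance of 70% to 89% for CT and 93% to 98% for syphilis, and modified Poisson with robust errors could then report an overwhelming effect from one or two infections.

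This rests on the assumed prevalences and on infection counts at full enrolment with a usable specimen from every infection. At the assumed infection rates, early closure (554 enrolled at the interim review, Protocol 1.2.8) and failed specimens would make the comparison smaller and empty arms more likely.

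Severity is low. The objective is secondary in the SAP and in Protocol 3.2.2, Protocol 10.2 calls the endpoint exploratory, and the primary efficacy, GC and *S. aureus* analyses are not affected.

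**What to change.** 1. In SAP 7.5.5.2, name one estimand and a matching model: relative risk by modified Poisson, as for syphilis. Make this change together with item 4, since modified Poisson is the model that gives the falsely narrow interval when an arm is empty.
2. In 7.5.5.2 and 7.5.5.3, state the unit of analysis and cluster on participant (GEE) whenever the model is fitted.
3. Always report resistant/tested by arm with exact (Clopper-Pearson) 95% limits. Use a participant-level unit such as any resistant infection after baseline, so that resistance emerging in a later infection is not dropped.
4. If either arm has zero or very few resistant cases, with the number fixed in advance, replace the model with Fisher's test or an exact risk difference. The trigger should not demand a minimum in both arms before any comparison is made, because resistance seen only under doxycycline is the signal of interest.
5. Separately, correct the arm order of the CT and syphilis counts in Protocol 10.2.

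The cost is wording only, with no new data. The downside is that sparse results will not be adjusted for site, and participant-level limits are wider than infection-level ones.
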